## 6.2 SUMMARIES OF CONDUCT OF STUDY

Summaries of study conduct will include all enrolled patients in the study. The number of patients who enroll, discontinue, or complete the study will be summarized. Reasons for discontinuations and premature study withdrawal will be listed and summarized. Enrollment and major protocol deviations will be listed and evaluated for their potential effects on the interpretation of study results.

## 6.3 SUMMARIES OF DEMOGRAPHIC AND BASELINE CHARACTERISTICS

Demographic and baseline characteristics (including, but not limited, to age, race/ethnicity, weight, type of malignancy, duration of malignancy, site of metastatic disease, baseline ECOG Performance Status, number of prior cancer regimens) will be summarized using means, standard deviations, medians, and ranges for continuous variables and proportions for categorical variables, as appropriate. Summaries will be presented overall and by dose level.

## 6.4 SAFETY ANALYSES

For safety analyses, the analysis population will include all enrolled patients who receive at least one dose of study medication.

Study treatment discontinuation and reasons for patient discontinuations from the study will be described and summarized. Study drug administration data will be listed and any dose modifications will be flagged.

### 6.4.1 Adverse Events

All adverse events occurring on or after treatment on Day 1 will be summarized by mapped term, appropriate thesaurus levels, and NCI CTCAE v4.0 toxicity grade.

All adverse events reported during the adverse event reporting period will be considered as treatment-emergent adverse events. Incidence rates will be summarized with frequency and percentage by mapped term, with all patients treated as the denominator, unless otherwise specified. In addition, adverse event incidence rates will also be summarized by severity and relationship to study drug. Treatment-related adverse events are those judged by the Investigator to be at least possibly related to the study drug.

Safety will be assessed through summaries of adverse events, changes in laboratory test results, and DHES0815A exposure. All patients who receive study treatment on Cycle 1, Day 1 will be included in the analyses.

Adverse event data will be listed by patient number and study day. Serious adverse events, including deaths, will be listed separately and will be summarized.

Relevant laboratory and vital sign (pulse rate, blood pressure, and temperature) data will be displayed by time, with NCI CTCAE v4.0 Grades 3 and 4 values identified, where appropriate. Additionally, all laboratory data will be summarized by NCI CTCAE v4.0.

Safety data will be accumulated up to the end of the patient's treatment period.

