**Table 1 Objectives and Corresponding Endpoints**

Safety Objective (Primary Study Objective)	Corresponding Endpoints
• To evaluate the safety and tolerability of escalating doses of DHES0815A administered by IV infusion every 3 weeks to patients with advanced or metastatic HER2-positive BC including estimation of the MTD, determination of the RP2D, and characterization of DLTs	

Occurrence and severity of adverse events including DLTs, with severity determined according to NCI CTCAE v4.0

Change from baseline in targeted vital signs

Change from baseline in targeted clinical laboratory test results, including ECGs

Number of cycles received and dose intensity

LVEF as assessed by ECHO or MUGA scan

Pharmacokinetic Objective	Corresponding Endpoint
• To characterize the DHES0815A pharmacokinetics when administered by IV infusion	

Concentration of three key PK analytes of DHES0815A (i.e., DHES0815A Total Antibody, acPBD-MA, and unconjugated PBD-MA, see Section 6.5) at specified timepoints

PK parameters of DHES0815A Total Antibody, acPBD-MA, and unconjugated PBD-MA

Activity Objective	Corresponding Endpoints
• To make a preliminary assessment of the anti-tumor activity of DHES0815A	

Objective response, defined as a complete response or partial response on two consecutive occasions <math>\geq 4</math> weeks apart, as determined by the investigator according to RECIST v1.1

Duration of response, defined as the time from the first occurrence of a documented objective response to disease progression or death from any cause, whichever occurs first, as determined by the investigator according to RECIST v1.1

Immunogenicity Objective	Corresponding Endpoints

 
To evaluate and characterize the immunogenic response to DHES0815A (by measuring anti-DHES0815A antibodies) administered by IV infusion, including the potential effects of ADAs on other outcome measures
 
	
 
Incidence of ADA formation to DHES0815A (anti-DHES0815A antibodies) during the study relative to the prevalence of ADA at baseline
 
Relationship between ADA status and safety, PK, biomarkers, or preliminary efficacy endpoints
 

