#### **4.5.4        Vital Signs**

Vital signs will include measurements of respiratory rate, heart rate, systolic and diastolic blood pressures while the patient is in a seated position, pulse oximetry, and temperature.

On Day 1 of Cycle 1 and on Day 1 of Cycle 2 and on any day of infusion where a 2-hour post-infusion observation period is warranted (see Section 4.3.2), vital signs will be assessed prior to infusion, every 15 ( $\pm$  5) minutes during infusion, at the end of infusion ( $\pm$  5 minutes), and every 30 ( $\pm$  10) minutes after the infusion for 2 hours. For all other days of infusion where a 30-minute post-infusion observation period is allowed (see Section 4.3.2), vital signs will be assessed prior to infusion, every 15 ( $\pm$  5) minutes during infusion, at the end of infusion ( $\pm$  5 minutes), and at 30 ( $\pm$  10) minutes after infusion. Oxygen saturation via pulse oximetry will be monitored at a minimum every 15 ( $\pm$  5) minutes during infusion from pretreatment to the end of the observation period. Additional monitoring should be performed if clinically indicated. Vital signs will be monitored at the timepoints specified in [Appendix 1](#).

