#### **5.1.1.7 Pulmonary Toxicity**

In GLP toxicology studies in cynomolgus monkeys, an increase in alveolar macrophages was observed after the administration of DHES0815A. Mild alveolar degeneration and fibroplasia was observed in nonclinical studies when cynomolgus monkeys received DHES0815A at dose levels higher than those given in the GLP toxicology studies. Cases of interstitial lung disease, including pneumonitis, some leading to acute respiratory distress syndrome or death, have been reported in patients receiving HER2-targeting drugs (i.e., trastuzumab, pertuzumab, trastuzumab emtansine). Signs and symptoms may include dyspnea, cough, fatigue, and pulmonary infiltrates. Patients with dyspnea at rest due to complications of advanced malignancy and comorbidities may be at risk of pulmonary events. Therefore, patients with clinically significant pulmonary symptoms or disease will be excluded from this study (see Section 4.1.2). Patients who develop new respiratory symptoms or imaging findings suggestive of pulmonary toxicity should be evaluated by a pulmonologist.

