### Schedule of Activities (cont.)

- d Patients who have not withdrawn consent or been lost to follow-up will be contacted 42 days after the last dose of study drug for information on adverse events and initiation of any subsequent anti-cancer therapies.
- e Medical history includes all clinically significant diseases, surgeries, cancer history (including prior cancer therapies and procedures), reproductive status, smoking history, and all medications used by the patient within 7 days preceding the screening visit (including prescription drugs, over-the-counter drugs, and herbal/homeopathic remedies and therapies). Demographic data includes age, sex, and self-reported race/ethnicity.
- f Complete physical examination should include evaluation of head, eyes, ears, nose, and throat, and the cardiovascular, dermatologic, musculoskeletal, respiratory, gastrointestinal, genitourinary, and neurologic systems.
- g Limited physical examination should include systems of primary relevance (i.e., cardiovascular, respiratory, and any system that might be associated with tumor assessment) and systems associated with symptoms. Patients should be evaluated weekly by limited physical examination through Cycle 4, on Day 1 and Day 8 Cycles 5–8, and at least on Day 1 of each Cycle beyond Cycle 8.
- h Vital signs include measurement of respiratory rate, heart rate, systolic and diastolic blood pressure while the patient is in a seated position, pulse oximetry, and temperature. On Day 1 of Cycle 1 and on Day 1 of Cycle 2, and on the day of infusion where a 2-hour post-infusion observation period is warranted (Section 4.3.2), vital signs will be assessed prior to infusion, every 15 ( $\pm$  5) minutes during infusion, at the end of infusion ( $\pm$  5 minutes), and every 30 ( $\pm$  10) minutes after the infusion for 2 hours. For all other days of infusion where a 30-minute post-infusion observation period is allowed, vital signs will be assessed prior to infusion, every 15 ( $\pm$  5) minutes during infusion, at the end of infusion ( $\pm$  5 minutes), and at 30 ( $\pm$  10) minutes after infusion. Oxygen saturation via pulse oximetry will be monitored at a minimum every 15 ( $\pm$  5) minutes during infusion from pre-treatment to the end of the observation period.

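### Section 6.4.1 plans no display of oxygen saturation or respiratory rate, although both are collected as vital signs and respiratory risks are named

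*Combined protocol and SAP*

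**What the plan says.** **Collection.** Section 4.5.4 says that vital signs "include measurements of respiratory rate, heart rate, systolic and diastolic blood pressures while the patient is in a seated position, pulse oximetry, and temperature". Appendix 1 footnote h repeats the list. For oximetry Section 4.5.4 adds a minimum frequency: "Oxygen saturation via pulse oximetry will be monitored at a minimum every 15" minutes (with a 5-minute tolerance) during infusion, running from pretreatment to the end of the observation period.

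**Endpoint.** Table 1 lists, under the primary safety objective, "Change from baseline in targeted vital signs". The word *targeted* is not defined in Table 1, the synopsis or Section 6.

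**Analysis.** Section 6.4.1 says: "Relevant laboratory and vital sign (pulse rate, blood pressure, and temperature) data will be displayed by time", with Grade 3 and 4 values identified where appropriate. The same section says that safety is assessed through summaries of adverse events, laboratory changes and exposure; vital signs are not in that sentence. Section 6 adds generally that data are summarized as warranted, by assigned dose level and cohort, with listings where samples are small.

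**Risks.** Section 5.1.1.7 reports for monkeys given doses above those of the GLP studies: "Mild alveolar degeneration and fibroplasia was observed in nonclinical studies". For the drug class it says: "Cases of interstitial lung disease, including pneumonitis, some leading to acute respiratory distress syndrome or death, have been reported in patients receiving HER2-targeting drugs". Section 5.1.1.8 describes vascular leak and effusions with related compounds. Section 5.1.1.10 lists dyspnea, wheezing and bronchospasm among the signs of infusion reactions.

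**The concern.** The two vital signs without a planned output are the two that bear most directly on the respiratory risks the protocol names. The protocol asks sites to read oxygen saturation repeatedly around each infusion, yet the plan commits to showing none of it.

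At stake is a modest shift in saturation shared across a dose level. In each patient it may look unremarkable and not be recorded as an adverse event. Only a summary by dose level and time would make the pattern visible. Section 3.3.3 itself says that small escalation cohorts limit what can be learned about dose and adverse events. A serial continuous measure is useful in that setting.

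**Working it through.** No figure in the plan is in dispute, so the main check is an item-by-item comparison, taking heart rate in Section 4.5.4 and pulse rate in Section 6.4.1 as the same measure.

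| Measurement | Collected (4.5.4, App. 1 note h) | Display named (6.4.1) |
|---|---|---|
| Heart or pulse rate | yes | yes |
| Systolic blood pressure | yes | yes |
| Diastolic blood pressure | yes | yes |
| Temperature | yes | yes |
| Respiratory rate | yes | no |
| Oxygen saturation | yes | no |

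Collected: 6. Display named: 4. No display named: 6 − 4 = 2.

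**Is another output planned elsewhere?** Sections 6 to 6.8 contain no listing, table or summary that names respiratory rate or oxygen saturation. Section 6.4.2 covers laboratory results only.

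**Is the list open or closed?** The parenthesis in Section 6.4.1 carries no *for example* or similar wording. Section 6.3 uses explicit open-list wording for baseline characteristics. The natural reading of Section 6.4.1 is a closed list.

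**Does the output match the endpoint?** Table 1 asks for change from baseline. Section 6.4.1 promises a display by time and does not mention change from baseline for any vital sign.

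**How much data is involved?** On Cycle 1 Day 1, with the 90-minute infusion of Section 4.3.2 and the timing in Section 4.5.4, the scheduled readings are:

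- before infusion: 1
- during infusion, at 15, 30, 45, 60 and 75 minutes: 5
- at the end of infusion: 1
- after infusion, at 30, 60, 90 and 120 minutes: 4

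Total: 1 + 5 + 1 + 4 = 11 readings of each measure per patient. Vital signs then continue weekly through Cycle 4 in the escalation stage (about 24–30 patients) and weekly through Cycle 2 in the expansion stage (up to about 25 patients), less often after that. These counts describe how much is collected without a planned display; they do not measure harm.

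**What would still be seen?** Section 5.3.5.6 requires an adverse event report if a vital-sign result comes with symptoms, changes study treatment, leads to an intervention or changed concomitant therapy, or is clinically significant in the investigator's judgment. What remains without a planned output is a change that meets none of these conditions.

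**The case against.** The strongest case against has four parts.

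1. *The endpoint may be met as written.* Table 1 promises targeted vital signs, not all vital signs, and the three named in Section 6.4.1 could be the targeted set. This is a possible reading, and the documents neither confirm nor exclude it. A reader might infer that a primary-objective endpoint goes unanalyzed; the text does not support that. It does support saying that the term is undefined.

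2. *The risks have other routes to detection.* Adverse event reporting applies as described above. Infusion reactions have a dedicated form for signs and symptoms (Section 5.3.5.1). Targeted examinations include the respiratory system (Section 4.5.3). Chest imaging is done at Cycles 2, 4, 6 and 8 and every three cycles after that (Appendix 1 footnote m), and Section 5.1.1.8 says it may be assessed for effusions. Section 5.1.1.7 sends new respiratory symptoms or suggestive imaging to a pulmonologist. All of this stands. A reader might infer that lung toxicity would go undetected; the documents do not support that.

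3. *Nothing forbids a further display.* Section 6 allows data to be summarized as warranted. This also stands, but it is permission and not a commitment, and the specific sentence in Section 6.4.1 points to a shorter list.

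4. *Escalation does not run on this display.* Section 3.1.1.2 names demographic, adverse event, laboratory, dosing and PK data for escalation decisions, and Section 4.2 adds the available cumulative safety data. A reader might infer that dose decisions are compromised by Section 6.4.1; they do not depend on it. Vital signs are not named in Section 3.1.1.2 either, so that review does not supply the missing output.

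**Conclusion.** The point holds as a reporting gap of minor to moderate weight. Two of six collected vital-sign measurements, both relevant to named risks, have no planned output, and the endpoint they may belong to is undefined. The practical loss is confined to changes in saturation or respiratory rate that are asymptomatic, not acted on and not judged clinically significant. The documents give no frequency for such changes, and none is assumed here.

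The conclusion rests on reading the parenthesis in Section 6.4.1 as a closed list and on the absence of any other named output in Section 6. If the sponsor intends the list as illustrative, the remedy is the same: say so and name the measures.

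There is no effect on sample size, DLT rules, escalation rules or the expansion stopping rules. The change counts as a free improvement.

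**What to change.** - In Section 6.4.1, change the parenthesis to: pulse rate, blood pressure, temperature, respiratory rate and oxygen saturation.
- State there, or in Table 1, that these are the targeted vital signs of the primary-objective endpoint.
- Commit to summarizing their change from baseline by dose level and timepoint.
- Optional: show the lowest oxygen saturation per patient on each infusion day. The documents do not require this display, and the point does not depend on it.

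The cost is a few words in the plan and a small number of extra displays from data already collected. No new assessment and no change in patient management follow from it.

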#### **6.4.2 Clinical Laboratory Results**

Normal ranges will be used to identify values that are outside the normal ranges, and abnormal laboratory results will be graded according to the NCI CTCAE v4.0.

A shift summary of baseline grade by maximum postbaseline NCI CTCAE grade will be presented, as appropriate. For each laboratory parameter, the baseline laboratory value will be defined as the last laboratory value collected on or prior to the date of the first dose of study drug.

Patients who develop toxicities of Grade  $\geq 3$  will be summarized. Laboratory test results not having NCI CTCAE grade will also be summarized. Parameters that have criteria available for both low and high values (e.g., hypocalcaemia vs. hypocalcemia) will be summarized for both criteria. Patients will only be counted once for each criterion.

#### **6.5 PHARMACOKINETIC ANALYSES**

The pharmacokinetics of DHES0815A will be characterized by measuring DHES0815A total antibody (all DARs including fully conjugated, partially deconjugated, and fully deconjugated anti-HER2 antibody) by ELISA, acPBD-MA by immunoaffinity LC-MS/MS, and unconjugated PBD-MA by LC-MS/MS. Two additional exploratory plasma PK samples (see [Appendix 2](#)) will be collected for catabolite and stability/biotransformation analyses. A baseline serum sample (Cycle 1, Day 1 only) may be used, depending upon review of DHES0815A PK/ADA data, to measure HER2 ECD, pertuzumab, trastuzumab, and/or trastuzumab emtansine levels in order to better

understand potential drug interferences or impact on pharmacokinetics. Individual and mean concentration of DHES0815A versus time data will be tabulated and plotted by dose level. The following PK parameters will be derived when appropriate as data allow:

- Total exposure (area under the concentration–time curve)
- Maximum observed serum concentration
- Minimum observed serum concentration
- Clearance
- Volume of distribution at steady state

Compartmental, non-compartmental, and/or population methods may be considered. Estimates for these parameters will be tabulated and summarized (mean, standard deviation, coefficient of variation, median, minimum, and maximum). Other parameters, such as accumulation ratio, terminal half-life, and dose proportionality, may also be calculated.

Additional PK analyses will be conducted as appropriate.

## **6.6 ACTIVITY ANALYSES**

Objective response will be summarized by dose level and cohort. Objective response is defined as a CR or PR, as determined by investigator assessment according to RECIST v1.1 and confirmed by repeat assessment  $\geq 4$  weeks after initial documentation. Patients with missing baseline or no response assessments will be classified as non-responders.

Among patients with an objective overall response, duration of response (DOR) will be defined as the time from the initial CR or PR to the time of disease progression or death, whichever occurs first. If a patient has not experienced disease progression or death, DOR will be censored at the day of the last tumor assessment showing no disease progression.

## **6.7 IMMUNOGENICITY ANALYSES**

Patients are considered to have treatment-induced ADA responses if they are ADA negative at baseline and develop an ADA response following DHES0815A administration. Patients are considered to have treatment-enhanced ADA if they are ADA positive at baseline and the titer of one or more postbaseline samples is at least 4-fold greater than baseline titer (i.e.,  $\geq 0.60$  titer units) following study drug administration. ADA incidence will be determined from the patients with treatment-induced and treatment-enhanced ADA.

Patients are considered to be negative for ADAs if they are ADA negative at all timepoints. Patients are considered to be treatment unaffected if they are ADA positive at baseline but do not have any postbaseline samples with a titer that is at least 4-fold

greater than the titer of the baseline sample. ADA prevalence will be determined from all patients with ADA-positive responses at baseline.

The immunogenicity analysis population will consist of all patients with at least one ADA assessment. Patients will be grouped according to treatment received or, if no treatment is received prior to study discontinuation, according to treatment assigned.

The relationship between ADA status and safety, efficacy, PK, activity, and biomarker endpoints will be analyzed and reported via descriptive statistics, as data allow.

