Patients in this study will be initially assessed for eligibility during the screening period (lasting  $\leq$  28 days). Following confirmation of eligibility, patients will receive DHES0815A by IV infusion on the first day of every cycle. A detailed PK evaluation will be performed during Cycle 1 and more limited PK assessments thereafter. Patients will be evaluated weekly by physical examination and by blood collections for routine hematologic and metabolic laboratory assessments for the first four cycles of DHES0815A treatment during dose escalation, the first two cycles during dose expansion, and less frequently thereafter. Cardiac ejection fraction (left ventricular ejection fraction [LVEF]) will be monitored by transthoracic echocardiogram (ECHO) or multiple-gated acquisition scan (MUGA) at baseline and in the last week (Days 15–21) of Cycles 1, 2, 4, and 6, and then after every four cycles thereafter. Ophthalmic examinations (best corrected visual acuity [BCVA] and anterior segment slit lamp examination with fluorescein) to monitor for visual and/or corneal changes will occur at baseline and during the last week (Days 15–21) of Cycles 2, 4, and 6, and every four cycles thereafter. Tumor assessment will occur at baseline and during the last week (Days 15–21) of every even-numbered cycle until Cycle 8 (i.e., at Cycles 2, 4, 6, and 8) and at every three cycles thereafter (i.e., at Cycles 11, 14, 17, etc.) until discontinuation or study termination.

Adverse events will be graded according to the National Cancer Institute Common Terminology Criteria for Adverse Events, Version 4.0 (NCI CTCAE v4.0). Patients deriving clinical benefit may be offered continued treatment with DHES0815A until disease progression or intolerable toxicity at the discretion of the investigator (see Section 3.1.1.4).

Disease status will be assessed using the Response Evaluation Criteria in Solid Tumors, Version 1.1 (RECIST v1.1) (Eisenhauer et al. 2009; see [Appendix 3](#)). Tumor status will be categorized as a complete response (CR), partial response (PR), stable disease, or progressive disease (PD), per RECIST v1.1. Objective response should be confirmed by repeat physical examination or image-based evaluation  $\geq$  4 weeks after the initial documentation, per RECIST v1.1 (see [Appendix 3](#)).

Blood samples will be collected for assessment of molecular and genetic biomarkers at baseline and end of study.

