## Appendix 2 Schedule of Pharmacokinetic and Immunogenicity Samples

Study Visit	Timepoint	DHES0815A PK a,b,c	Anti-DHES0815A Antibody (ADA) d
Cycle 1, Day 1	Pre-infusion	x e	x
	30 minutes ( $\pm$ 15 minutes) post-EOI	x	
	4 hours ( $\pm$ 15 minutes) post-EOI	x	
Cycle 1, Day 2	24 hours ( $\pm$ 2 hours) post-EOI	x	
Cycle 1, Day 3	48 hours ( $\pm$ 2 hours) post-EOI	x	
Cycle 1, Day 8	7 days ( $\pm$ 1 day) post-EOI	x	
Cycle 1, Day 11	10 days ( $\pm$ 1 day) post-EOI	x	
Cycle 1, Day 15	14 days ( $\pm$ 1 day) post-EOI	x	
Cycle 1, Day 17	16 days ( $\pm$ 1 day) post-EOI	x	
Cycles 2–4, Day 1	Pre-infusion	x	x
	30 minutes ( $\pm$ 15 minutes) post-EOI	x	
Cycles 2–4, Day 8	7 days ( $\pm$ 1 day) post-EOI	x	
Cycles 2–4, Day 15	14 days ( $\pm$ 1 day) post-EOI	x	
Study treatment discontinuation visit	Within 42 days after last infusion	x	x

acPBD-MA=antibody-conjugated PBD-MA; ADA=anti-drug antibody; ECD=extracellular domain; EOI=end of infusion; NA=not applicable; PBD-MA=pyrrolo[2,1-c][1,4]benzodiazepine-monoamide; PK=pharmacokinetic; QTcF=QT interval corrected through use of Fridericia's formula.

Note: Samples will be submitted to a central laboratory. *Pre-infusion laboratory samples should be drawn within 4 hours before the start of infusion.*

- a For PK sample collection instructions, please refer to the laboratory manual. In the event that a serious adverse event or a dose-limiting toxicity occurs at a time when a PK sample is not scheduled, every effort should be made to collect a PK sample as an unscheduled event.
- b Clinical plans include measurement of the following analytes for PK assessment of DHES0815A: DHES0815A total antibody (serum, SER-PK), acPBD-MA (plasma, PL-PK1), and unconjugated PBD-MA (plasma, PL-PK2). Two additional exploratory PK samples (plasma, PL-PK-EXP1, PL-PK-EXP2) will be collected for catabolite and stability/biotransformation analyses.
- c If an increase in QTcF is observed in an ECG measurement as described in Section 4.5.7 and a PK sample is not scheduled at that timepoint, then an unscheduled DHES0815A PK sample should be obtained.
- d Serum samples for assessment of anti-DHES0815A antibodies (ADA) will be drawn at baseline (prior to dosing on Day1, Cycle 1), before dosing on Day 1 of Cycles 2–4, at study completion/early discontinuation visit.

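### Section 6.7 groups patients as ever or never ADA-positive although the number of ADA samples depends on time on treatment, which biases the response comparison in favour of ADA-positive patients

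*Combined protocol and SAP*

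**What the plan says.** Section 6.7 defines treatment-induced ADA as being "ADA negative at baseline and develop an ADA response following DHES0815A administration", with no time window. Treatment-enhanced ADA requires that "the titer of one or more postbaseline samples is at least 4-fold greater than baseline titer". On the other side, "Patients are considered to be negative for ADAs if they are ADA negative at all timepoints". One later positive sample is therefore enough to make a baseline-negative patient positive. The population rule is broad: "The immunogenicity analysis population will consist of all patients with at least one ADA assessment". No post-baseline sample is needed.

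Appendix 2, footnote d, sets the sampling: baseline, then "before dosing on Day 1 of Cycles 2–4, at study completion/early discontinuation visit".

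Table 1 lists the comparison as an endpoint under the Immunogenicity Objective: "Relationship between ADA status and safety, PK, biomarkers, or preliminary efficacy endpoints". The objectives labelled exploratory appear separately. Section 6.7 repeats the comparison and makes it descriptive: "The relationship between ADA status and safety, efficacy, PK, activity, and biomarker endpoints will be analyzed and reported via descriptive statistics, as data allow".

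Time on treatment depends on outcome. Section 3.1 states: "Patients deriving clinical benefit may be offered continued treatment with DHES0815A until disease progression or intolerable toxicity". Section 6.6 counts patients with no response assessment as non-responders, and Section 6.4.1 reports crude adverse event incidence with all treated patients as the denominator. The plan gives no landmark, time-dependent ADA status, minimum number of samples or exposure adjustment.

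**The concern.** ADA status is built from data collected after treatment starts, and the amount of data depends on the outcome it is compared with. This is a bias of the immortal-time type. A patient has to remain on treatment to be tested more often, and remaining on treatment goes with response. Two rules add to it. A patient with only a negative baseline sample can count as ADA-negative, and a patient who leaves before any scan counts as a non-responder. Both push early leavers into the same cell of the table.

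What is at stake is how a listed endpoint is read. An apparent association of ADA with better response could arise from the sampling schedule alone. Because the bias raises response in ADA-positive patients, it would also offset a true reduction in response of similar size.

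**Working it through.** The plan states no ADA incidence, effect size or power for this comparison, so there is no figure of its own to reproduce.

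**Sample count (Appendix 2).** With last dosed cycle L, the number of post-baseline samples is k = min(L − 1, 3) + 1, the final 1 being the discontinuation visit. This gives k = 1, 2, 3 and 4 for L = 1, 2, 3 and 4 or more, or one fewer if the discontinuation sample is missed. The count is capped at four.

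**Link to response (Appendix 1, Section 6.6).** The first on-treatment scan falls on Days 15–21 of Cycle 2, which are study Days 36–42. Confirmation at least 28 days later falls on Day 64 or after, and Cycle 4 Day 1 is Day 64. A confirmed responder who stays on schedule therefore has all three on-treatment samples plus discontinuation, so k = 4. A patient who stops for progression at the first scan has Cycle 2 Day 1 plus discontinuation, so k = 2.

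**Assumptions.** ADA is independent of response, and each post-baseline sample turns positive with constant probability q of 5%, 10% or 20%. The response rate is 40%, borrowed from the confidence interval illustration in Section 6.1.2. A fraction f of non-responders has k = 2 and the rest have k = 4.

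**Formulas.** P(ever positive | k) = 1 − (1 − q)^k. Write a for k = 4, b₂ for k = 2, and b = f·b₂ + (1 − f)·a for non-responders. Then:

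- Response if ADA-positive = 0.4a / (0.4a + 0.6b)
- Response if ADA-negative = 0.4(1 − a) / [0.4(1 − a) + 0.6(1 − b)]

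| q | a | b₂ | f = 1: ADA+ vs ADA− | Gap (points) | f = 0.5: ADA+ vs ADA− | Gap (points) |
|---|---|---|---|---|---|---|
| 5% | 0.185 | 0.098 | 55.9% vs 37.6% | 18.3 | 46.6% vs 38.7% | 7.9 |
| 10% | 0.344 | 0.190 | 54.7% vs 35.1% | 19.6 | 46.2% vs 37.4% | 8.8 |
| 20% | 0.590 | 0.360 | 52.2% vs 29.9% | 22.3 | 45.3% vs 34.2% | 11.1 |

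For f from 0.3 to 0.7 the gap runs from about 4.5 to 15.5 points. The true difference is zero throughout.

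**Check by simulation.** This used 400,000 patients per scenario, no ADA effect, 30% response, 3% to 10% conversion, 30% to 70% of non-responders stopping after Cycle 1 or 2, and the discontinuation sample obtained in 70% to 100%. If only the sample count matters, the false gap is about 4 to 14 points. If ADA instead arises at a constant rate per cycle, persists and is detected at discontinuation, it is about 15 to 31 points. All 36 scenarios moved in the same direction. Classifying ADA at Cycle 4 Day 1 among patients still on treatment brought the gap to within 0.6 points of zero, which is simulation error.

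**The case against.** The strongest points on the other side concern size and scope, and most of them stand.

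- **Size.** A reader might take 18 to 22 points as the expected bias. That figure requires every non-responder to leave with two samples. Section 3.1.1.4 lets patients with stabilised disease or clinical signs of benefit continue, and these non-responders can reach four samples.
- **Length of stay.** A reader might infer that each extra cycle adds a chance of positivity. After Cycle 4 Day 1 only the discontinuation sample remains, so patients with 4 and 20 cycles both have at most four.
- **Duration of response.** This is defined among responders, who on schedule already have all three on-treatment samples. Only the timing of the last sample differs.
- **PK.** The intensive profile is in Cycle 1, before any scheduled post-baseline ADA sample. Later pre-dose PK and ADA samples share the same visits. The documents do not support a claim that loss of exposure would be hidden.
- **Adverse events.** It is tempting to say ADA-positive patients will show more events because they are observed longer. Toxicity can also end treatment early and reduce the number of samples, so the net direction is not determined.
- **Noise.** At q = 5% and f = 1, about 7.3 of 55 patients would be ADA-positive. An 80% normal interval for the response difference has half-width 1.28 × √(0.559 × 0.441/7.3 + 0.376 × 0.624/47.7), about 25 points, which is wider than the bias.

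The plan is also descriptive, Section 6 uses listings when numbers are small, and Section 6.1.2 disclaims power and type I error. This lowers the consequence, but a descriptive table split by ever-positive status carries the same distortion.

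**Conclusion.** The concern holds for response by ADA status. As written, Section 6.7 and Appendix 2 produce a comparison that favours ADA-positive patients in expectation when ADA has no effect. Under the 40% response and 5% to 20% conversion assumptions, the false difference is about 8 to 11 points if half of non-responders leave with two samples, with 18 to 22 points as the upper case of that model. The ADA rates and drop-off patterns are assumed. The direction follows from the definitions and the schedule, provided responders generally stay on treatment to Cycle 4.

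Crude adverse event incidence by ADA group is confounded by time on treatment, with unknown sign. Effects on duration of response and PK are small or indirect. No MTD, RP2D or stopping rule uses ADA status, so the matter is confined to the immunogenicity endpoint. It is an inexpensive improvement and not a threat to the primary objective.

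**What to change.** Amend Section 6.7 as follows.

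1. Compare pre-dose PK by the ADA result at the same Cycle 2–4 Day 1 visit, within dose level.
2. Report adverse events per unit of exposure before and after the first positive sample.
3. For response, use ADA status at Cycle 4 Day 1 among patients still on treatment. Show responses that began before and after that landmark separately, count any duration-of-response comparison from the landmark, and state that the result is conditional on remaining on treatment.
4. Require at least one post-baseline sample for ADA incidence and for comparisons by ADA status. Report the number of ADA samples and time on treatment by ADA group.
5. Give ever-positive versus negative comparisons of response and adverse events as listings only.

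No new samples or visits are needed. The cost is analysis programming and fewer patients in the landmark comparison. That comparison also says nothing about ADA effects in patients who stop before Cycle 4, including any whose early progression was itself related to ADA, and the text should say so.
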